12.1 Study Oversight

This protocol is monitored at several levels, as described in this section. The Protocol Principal Investigator is responsible for monitoring the conduct and progress of the clinical trial, including the ongoing review of accrual, patient-specific clinical and laboratory data, and routine and serious adverse events; reporting of expedited adverse events; and accumulation of reported adverse events from other trials testing the same drug(s). The Protocol Principal Investigator and statistician have access to the data at all times through the CTMS web-based reporting portal.

The Protocol Principal Investigator will have, at a minimum, quarterly conference calls with the Study Investigators to review accrual, progress, and pharmacovigilance. Decisions to proceed to the second stage of a Phase 2 trial will require sign-off by the Protocol Principal Investigator and the Protocol Statistician.

All Study Investigators at participating sites who register/enroll patients on a given protocol are responsible for timely submission of data via Medidata Rave and timely reporting of adverse events for that particular study. This includes timely review of data collected on the electronic CRFs submitted via Medidata Rave.

All studies are also reviewed in accordance with the enrolling institution's data safety monitoring plan.

12.2 Data Reporting

Data collection for this study will be done exclusively through Medidata Rave. Access to the trial in Rave is granted through the iMedidata application to all persons with the appropriate roles assigned in the Regulatory Support System (RSS). To access Rave via iMedidata, the site user must have an active CTEP IAM account (check at < <https://ctepcore.nci.nih.gov/iam> >) and the appropriate Rave role (Rave CRA, Read-Only, CRA, Lab Admin, SLA or Site Investigator) on either the

LPO or participating organization roster at the enrolling site. To hold Rave CRA role or CRA Lab Admin role, the user must hold a minimum of an AP registration type. To hold the Rave Site Investigator role, the individual must be registered as an NPIVR or IVR. Associates can hold read-only roles in Rave.

Upon initial site registration approval for the study in RSS, all persons with Rave roles assigned on the appropriate roster will be sent a study invitation e-mail from iMedidata. To accept the invitation, site users must log into the Select Login (<https://login.imedidata.com/selectlogin>) using their CTEP-IAM user name and password, and click on the “accept” link in the upper right-corner of the iMedidata page. Please note, site users will not be able to access the study in Rave until all required Medidata and study specific trainings are completed. Trainings will be in the form of electronic learnings (eLearnings), and can be accessed by clicking on the link in the upper right pane of the iMedidata screen.

Users that have not previously activated their iMedidata/Rave account at the time of initial site registration approval for the study in RSS will also receive a separate invitation from iMedidata to activate their account. Account activation instructions are located on the CTSU website, Rave tab under the Rave resource materials (Medidata Account Activation and Study Invitation Acceptance). Additional information on iMedidata/Rave is available on the CTSU members’ website under the Rave tab or by contacting the CTSU Help Desk at [name] or by e-mail at [contact].

12.2.1 Method

This study will be monitored by the Clinical Trials Monitoring Service (CTMS). Data will be submitted to CTMS at least once every two weeks via Medidata Rave (or other modality if approved by CTEP). Information on CTMS reporting is available at: <http://www.theradex.com/clinicalTechnologies/?National-Cancer-Institute-NCI-11>. On-site audits will be conducted on an 18-36 month basis as part of routine cancer center site visits. More frequent audits may be conducted if warranted by accrual or due to concerns regarding data quality or timely submission. For CTMS monitored studies, after users have activated their accounts, please contact the Theradex Help Desk at [contact] or by email at [contact] for additional support with Rave and completion of CRFs.

12.2.2 Responsibility for Data Submission

For ETCTN trials, it is the responsibility of the PI(s) at the site to ensure that all investigators at the ETCTN Sites understand the procedures for data submission for each ETCTN protocol and that protocol specified data are submitted accurately and in a timely manner to the CTMS via the electronic data capture system, Medidata Rave.

Data are to be submitted via Medidata Rave to CTMS on a real-time basis, but no less than once every 2 weeks. The timeliness of data submissions and timeliness in resolving data queries will be tracked by CTMS. Metrics for timeliness will be followed and assessed on a quarterly basis. For the purpose of Institutional Performance Monitoring, data will be considered delinquent if it is greater than 4 weeks past due.

Data from Medidata Rave and CTEP-AERS is reviewed by the CTMS on an ongoing basis as data is received. Queries will be issued by CTMS directly within Rave. The queries will appear on the Task Summary Tab within Rave for the CRA at the ETCTN to resolve. Monthly web-based reports are posted for review by the Drug Monitors in the IDB, CTEP. Onsite audits will be conducted by the CTMS to ensure compliance with regulatory requirements, GCP, and NCI policies and procedures with the overarching goal of ensuring the integrity of data generated from NCI-sponsored clinical trials, as described in the ETCTN Program Guidelines, which may be found on the CTEP (http://ctep.cancer.gov/protocolDevelopment/electronic_applications/adverse_events.htm) and CTSU websites.

An End of Study CRF is to be completed by the PI, and is to include a summary of study endpoints not otherwise captured in the database, such as (for phase 1 trials) the recommended phase 2 dose (RP2D), and a description of any dose-limiting toxicities (DLTs). CTMS will utilize a core set of eCRFs that are Cancer Data Standards Registry and Repository (caDSR) compliant (<http://cbiit.nci.nih.gov/ncip/biomedical-informatics-resources/interoperability-and-semantics/metadata-and-models>). Customized eCRFs will be included when appropriate to meet unique study requirements. The PI is encouraged to review the eCRFs, working closely with CTMS to ensure prospectively that all required items are appropriately captured in the eCRFs prior to study activation. CTMS will prepare the eCRFs with built-in edit checks to the extent possible to promote data integrity.

CDUS data submissions for ETCTN trials activated after March 1, 2014, will be carried out by the CTMS contractor, Theradex. CDUS submissions are performed by Theradex on a monthly basis. The trial's lead institution is responsible for timely submission to CTMS via Rave, as above.

Further information on data submission procedures can be found in the ETCTN Program Guidelines (http://ctep.cancer.gov/protocolDevelopment/electronic_applications/adverse_events.htm).

12.2.3 Data Submission for PRO-CTCAE assessments

Electronic collection of PRO-CTCAE through the ePRO is source documentation. The surveys are not stored on the devices. Rather, each survey is available for a window of 48 hours. Once the patient submits the survey, the responses go directly into the RAVE database and no longer are stored on the device. The site CRAs can access the RAVE workbench and see if the patient has completed all the questions and the date of completion.

There are no other records to audit or review.

12.3 CTEP Multicenter Guidelines

12.4 Collaborative Agreements Language

The agent(s) supplied by CTEP, DCTD, NCI used in this protocol is/are provided to the NCI under a Collaborative Agreement (CRADA, CTA, CSA) between the Pharmaceutical Company(ies) (hereinafter referred to as “Collaborator(s)”) and the NCI Division of Cancer Treatment and Diagnosis. Therefore, the following obligations/guidelines, in addition to the provisions in the “Intellectual Property Option to Collaborator”

(http://ctep.cancer.gov/industryCollaborations2/intellectual_property.htm) contained within the terms of award, apply to the use of the Agent(s) in this study:

1. Agent(s) may not be used for any purpose outside the scope of this protocol, nor can Agent(s) be transferred or licensed to any party not participating in the clinical study. Collaborator(s) data for Agent(s) are confidential and proprietary to Collaborator(s) and shall be maintained as such by the investigators. The protocol documents for studies utilizing Agents contain confidential information and should not be shared or distributed without the permission of the NCI. If a copy of this protocol is requested by a patient or patient’s family member participating on the study, the individual should sign a confidentiality agreement. A suitable model agreement can be downloaded from: <http://ctep.cancer.gov>.
2. For a clinical protocol where there is an investigational Agent used in combination with (an)other Agent(s), each the subject of different Collaborative Agreements, the access to and use of data by each Collaborator shall be as follows (data pertaining to such combination use shall hereinafter be referred to as "Multi-Party Data"):
 - a. NCI will provide all Collaborators with prior written notice regarding the existence and nature of any agreements governing their collaboration with NCI, the design of the proposed combination protocol, and the existence of any obligations that would tend to restrict NCI's participation in the proposed combination protocol.
 - b. Each Collaborator shall agree to permit use of the Multi-Party Data from the clinical trial by any other Collaborator solely to the extent necessary to allow said other Collaborator to develop, obtain regulatory approval or commercialize its own Agent.
 - c. Any Collaborator having the right to use the Multi-Party Data from these trials must agree in writing prior to the commencement of the trials that it will use the Multi-Party Data solely for development, regulatory approval, and commercialization of its own Agent.
3. Clinical Trial Data and Results and Raw Data developed under a Collaborative Agreement will be made available to Collaborator(s), the NCI, and the FDA, as appropriate and unless additional disclosure is required by law or court order as described in the IP Option to Collaborator (http://ctep.cancer.gov/industryCollaborations2/intellectual_property.htm). Additionally, all Clinical Data and Results and Raw Data will be collected, used and

disclosed consistent with all applicable federal statutes and regulations for the protection of human subjects, including, if applicable, the *Standards for Privacy of Individually Identifiable Health Information* set forth in 45 C.F.R. Part 164.

4. When a Collaborator wishes to initiate a data request, the request should first be sent to the NCI, who will then notify the appropriate investigators (Group Chair for Cooperative Group studies, or PI for other studies) of Collaborator's wish to contact them.
5. Any data provided to Collaborator(s) for Phase 3 studies must be in accordance with the guidelines and policies of the responsible Data Monitoring Committee (DMC), if there is a DMC for this clinical trial.
6. Any manuscripts reporting the results of this clinical trial must be provided to CTEP by the Group office for Cooperative Group studies or by the principal investigator for non-Cooperative Group studies for immediate delivery to Collaborator(s) for advisory review and comment prior to submission for publication. Collaborator(s) will have 30 days from the date of receipt for review. Collaborator shall have the right to request that publication be delayed for up to an additional 30 days in order to ensure that Collaborator's confidential and proprietary data, in addition to Collaborator(s)'s intellectual property rights, are protected. Copies of abstracts must be provided to CTEP for forwarding to Collaborator(s) for courtesy review as soon as possible and preferably at least three (3) days prior to submission, but in any case, prior to presentation at the meeting or publication in the proceedings. Press releases and other media presentations must also be forwarded to CTEP prior to release. Copies of any manuscript, abstract and/or press release/ media presentation should be sent to:

Email: [contact]

The Regulatory Affairs Branch will then distribute them to Collaborator(s). No publication, manuscript or other form of public disclosure shall contain any of Collaborator's confidential/proprietary information.

13. STATISTICAL CONSIDERATIONS

13.1 Study Design/Endpoints

13.1.1 Primary Endpoint: The primary endpoint of this study is overall response rate as determined by RECIST 1.1.

13.1.2 Secondary Endpoints: Secondary endpoints include progression-free and overall survival, overall response according to irRC, and assessments of safety.

Clinical laboratory tests, vital signs and weight measurements, physical exams, performance status evaluations, imaging scans and any other medically indicated assessments, including subject interviews, will be performed to detect new abnormalities and deteriorations of any pre-existing conditions.

13.2 Endpoint Definitions

13.2.1 Primary Endpoint

At each restaging, patients will be classified as achieving one of the following according to RECIST criteria: complete response (CR), partial response (PR), stable disease (SD), progressive disease (PD), or unevaluable for response, which includes early death from malignancy, toxicity, or other causes in addition to missing or unknown response. Best overall response will be calculated as the best response recorded from the date of randomization for each patient, taking as reference for progressive disease the smallest measurements recorded since the start of treatment. Objective response rate (ORR) is defined as the proportion of patients within a treatment arm who have a best response of either CR or PR. The denominator used to calculate ORR within a treatment will be the number of patients randomized to the respective treatment arm. All randomized patients will be used in randomized comparisons across arms. For single arm evaluation of response, all patients who started treatment will be considered evaluable.

13.2.2 Secondary Endpoints

Progression-free survival (PFS): Time from date of randomization until objective disease progression (per RECIST) or death, whichever occurs first. For patients without progression, follow-up will be censored at the date of last adequate restaging, unless death occurs within 12 weeks following the date last known progression-free, in which case the death will be counted as a PFS event.

Overall survival (OS): Time from randomization to death from any cause. For patients lost to follow-up or who have no documentation of death at the time of final analysis, follow-up will be censored at the date of last assessment of vital status.

Objective Response per Immune-Related Response Criteria (irORR): The proportion of patients within a treatment arm who have a best response of irCR or irPR according to Immune-Related Response Criteria. The denominator used to calculate irORR within each treatment will be the

number of patients randomized to the respective treatment arm.

13.3 Randomization

13.3.1 NSCLC

Patients enrolled in the NSCLC cohort will be randomly assigned in equal proportions to therapy with MEDI4736(durvalumab)/tremelimumab alone, MEDI4736(durvalumab)/tremelimumab with low-dose RT, or MEDI4736(durvalumab)/tremelimumab with high-dose RT. Forty patients will be assigned to each of the three therapies (120 in total).

13.3.2 Colorectal Cancer

Patients enrolled in the colorectal cancer cohort will be randomly assigned in equal proportions to either MEDI4736(durvalumab)/tremelimumab with low-dose RT or MEDI4736(durvalumab)-tremelimumab with high-dose RT. A total of 60 patients will be enrolled.

For each disease cohort, the randomization will follow a permuted block scheme with random block sizes of 3 or 6 for cohort 1 and 2 or 4 for cohort 2. The randomization schemes will be developed by the trial statistician and coordinated via CTEP.

13.4 Sample Size/Accrual

13.4.1 Sample Size

NSCLC: Best overall response rate is the endpoint on which the sample size for cohort 1 is based. We estimate an overall response rate of approximately 5% for the combination of MEDI4736 and tremelimumab alone based on a comparison of preliminary response rates from patients treated with dual checkpoint blockade of PD-1 and CTLA-4 (Hellman et al. ASCO 2016) as compared with PD-1 inhibitor monotherapy [6]. Two, pair-wise comparisons of therapy with high- or low-dose radiation against the control of MEDI4736(durvalumab)/tremelimumab alone will be conducted. Since a positive outcome for each comparison in this trial is the superiority of MEDI4736(durvalumab)/tremelimumab with high- or low-dose RT compared with MEDI4736(durvalumab)/tremelimumab alone, we propose one-sided chi-squared tests for the null hypothesis of equality of the response rates with a 10% type-I error for each comparison. To assess for early evidence of futility or superiority of MEDI4736(durvalumab)/tremelimumab plus RT, each pairwise comparison will be based on a group sequential design with O'Brien-Fleming stopping boundaries for superiority and Gamma family boundaries ($\gamma=1$) for futility.

When the total sample size in each comparison is 80 patients (40 per arm), a chi-squared test will have 81% power to detect a difference between a 5% response rate and 22% response rate. Interim and final analyses will be conducted after 40 and 80 patients have objective response classifications (corresponding to 50% and 100% of the total information). The critical values $z_{SEP}^{[1]}$ of the test statistic for superiority of MEDI4736(durvalumab)/tremelimumab with RT in each comparison for the interim and final analyses would be 2.054 and 1.317, corresponding to nominal significance $z_{SEP}^{[1]}$ levels of 0.02 and 0.094, respectively. If the p-value at the interim analysis is greater than 0.463 (i.e., the test statistic is less than 0.0922), there will be insufficient evidence to reject $z_{SEP}^{[1]}$ the null hypothesis and the trial for that comparison (and enrollment to the respective RT arm)

will stop early for futility. Under this design, the probability of stopping for futility at the ^[1]_[SEP] interim analysis is 0.56 if the null hypothesis is true. Sample size and power calculations were conducted using EaST 5.4. Note that enrollment to the MEDI4736(durvalumab)/tremelimumab-alone arm will continue as long as enrollment continues in at least one RT arm.

Colorectal Cancer: Best overall response rate is the endpoint on which the sample size is based for cohort 2. There is a low historical response rate in microsatellite stable colorectal cancer [14]; therefore, we will employ two, parallel, Simon optimal two-stage designs to identify therapy combinations worthy of further study in this patient population. A promising response rate in this population would be 20%. Sixty patients will be randomly assigned to high-dose or low-dose radiotherapy plus MEDI4736(durvalumab)/tremelimumab (30 per therapy). The high-dose and low-dose designs will be conducted separately. Ten patients will be enrolled in the first stage for each therapy. If there is at least one response among the first ten patients, then an additional 20 patients will be enrolled to that treatment arm for a total of 30 patients in each comparison. If four or more patients in a comparison have response then that treatment combination would be considered promising. Each design has a type-I error of 5% (target alpha=0.10) and 80% power to detect a difference between a null rate of 5% and a promising response rate of 20%. If the null hypothesis is true, the probability is 0.60 that accrual in that treatment arm will stop at the end of the first stage. If the cohort combining LDFRT is stopped early for futility, we will review the data and possibly amend the protocol at that time.

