13.7 Analysis of Primary Endpoints

NSCLC: The proportion of patients with response (CR or PR according to RECIST) will be compared for each pair-wise comparison of RT-containing therapy and control using chi-squared tests. The difference between the proportions responding will be presented with a 90% confidence interval.

Colorectal Cancer: Response rates within each two-stage design will be calculated and presented with one-sided 90% confidence intervals estimated using the method of Atkinson and Brown, which allows for the two-stage design.

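### NSCLC primary test: at the planned 5% response rate the 2.054/1.317 chi-squared rule has an exact type I error of 10.2% to 12.0% against the stated 10%, and the 0.56 futility probability does not match its boundary

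*Combined protocol and SAP*

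**What the plan says.** Section 13.4.1 (NSCLC) bases the design on the control-arm assumption "We estimate an overall response rate of approximately 5% for the combination of MEDI4736 and tremelimumab alone". For the comparison of each radiation arm with control, the plan reads: "we propose one-sided chi-squared tests for the null hypothesis of equality of the response rates with a 10% type-I error for each comparison". Its power statement is: "When the total sample size in each comparison is 80 patients (40 per arm), a chi-squared test will have 81% power". The alternative behind that figure is a response rate of 22% with radiation against 5% without.

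There is one interim look at half the information, which Section 4.3.2 puts at 20 patients per arm. The superiority critical values "for the interim and final analyses would be 2.054 and 1.317". A comparison stops for futility if the interim statistic is below 0.0922, and the plan gives the chance of that in these words: "interim analysis is 0.56 if the null hypothesis is true".

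Section 13.7 says that the response proportions "will be compared for each pair-wise comparison of RT-containing therapy and control using chi-squared tests", with a 90% confidence interval for the difference. Neither section names a continuity correction or an exact method. Neither gives the size of the test at a 5% response rate, or says what happens at the interim if neither arm has a responder, when the statistic is undefined.

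**The concern.** The critical values come from normal theory. At a 5% rate the expected number of responders per arm is 20 × 0.05 = 1 at the interim and 40 × 0.05 = 2 at the end. With counts that small, the pooled statistic takes only a few values near the cut-off, so the actual error rate can differ from the nominal one and needs an exact check. The primary decision rule could then miss its stated 10% at its own planning assumption, and the quoted futility probability could mislead whoever reviews the interim.

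**Working it through.** **Inputs.** From 13.4.1: null rate 5%, alternative 22% vs 5%, 40 per arm, one-sided 10%, boundaries 2.054 and 1.317, futility below 0.0922. From 4.3.2: 20 per arm at the interim. From 13.2.1: all randomized patients are in the denominator, so no dropout adjustment applies.

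**Statistic.** z = (x/n − y/n) / √[p̄(1 − p̄)·2/n], with p̄ = (x + y)/(2n), x responders on radiation and y on control, uncorrected.

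**Step 1: reproduce the plan's figures by normal theory.** The two looks are treated as bivariate normal with correlation √0.5.
- Power for 5% vs 22% with futility applied is 80.3% (pooled variance) or 82.2% (unpooled). These bracket the stated 81%, so it is reproduced.
- Type I error is 0.0999 if futility is ignored and 0.0942 if it is applied. So 1.317 was apparently calibrated with futility non-binding.

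**Step 2: outcomes that win at the final look.**
- 2/40 vs 0/40: p̄ = 2/80 = 0.025, so z = 0.05/√(0.025 × 0.975/20) = 0.05/0.0349 = 1.432. This exceeds 1.317 and is a win (one-sided p = 0.076; one-sided Fisher p = 0.247).
- 4/40 vs 1/40: p̄ = 5/80 = 0.0625, so z = 0.075/√(0.0625 × 0.9375/20) = 0.075/0.0541 = 1.386. This is also a win (Fisher p = 0.179).

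**Step 3: exact enumeration** of Binomial(20) + Binomial(20) in each arm.

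| Reading of the interim rule | Interim win | Final win | Type I error at 5% | Power, 5% vs 22% |
|---|---|---|---|---|
| Futility followed, 0/20 vs 0/20 stops | 0.0058 | 0.0963 | 10.2% | 83.4% |
| Futility followed, 0/20 vs 0/20 continues | 0.0058 | 0.1093 | 11.5% | 83.6% |
| Futility non-binding | 0.0058 | 0.1144 | 12.0% | 86.3% |

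A simulation of 2 million trials gave 10.2% for the first row and 12.0% for the third. The 2/40 vs 0/40 result makes up 0.0270/0.1021 = 26% of false wins in the first row and 0.0357/0.1202 = 30% in the third. The non-binding figure falls to 11.1% at a common rate of 10% and 9.9% at 25%, so the excess is largest near the planning rate.

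**Step 4: futility probability under the null.**
- Normal theory: P(Z < 0.0922) = 0.537. Adding the chance of crossing 2.054, which is 0.020, gives 0.557. The stated 0.56 therefore appears to be total early stopping.
- Exact at 5%: with 20 per arm, z is below 0.0922 only when the radiation arm has no more responders than control. The chance of a tie is 0.310 and of fewer is (1 − 0.310)/2 = 0.345, so the sum is 0.655. That counts 0/20 vs 0/20 as futile, which has probability 0.95^40 = 0.129. If that case continues, the figure is 0.527.

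**Step 5: alternative final cut-offs, interim rules unchanged.** Ranges span the three readings.

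| Final cut-off | Type I error at 5% | Largest over common rates 0.5–50% | Power | 2/40 vs 0/40 wins? |
|---|---|---|---|---|
| 1.40 | 8.2–9.6% | 10.4%, at about 3–4% | 80.9–83.3% | yes |
| 1.44 | 5.5–6.0% | 8.7% | 80.5–82.8% | no |

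The 10.4% for 1.40 arises if futility is non-binding or 0/20 vs 0/20 continues. With futility followed and 0/20 vs 0/20 stopping, the largest value is 8.9%.

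**The case against.** The strongest reply is that 13.4.1 says a comparison crossing the futility boundary will stop. Taken literally, with 0/20 vs 0/20 stopping, the error is 10.2%, a 0.2-point excess. That is ordinary discreteness in a phase 2 screening test at a lenient level, and exact power of 83.4% exceeds the stated 81%. This stands: a reader might infer that the rule simply has a 12% error rate, or that it fails to control error at all, and the documents support neither without a condition. But 1.317 yields 10% by normal theory only when futility is ignored, and the 0/20 vs 0/20 case is left open, so 11.5% and 12.0% are also live readings.

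A second reply is that a continuity correction may be intended. It would bring the error down to 1.7–2.3%, but power would be 68–74%, which does not fit 81%. The uncorrected test is an inference, but it is the reading that fits.

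A third concerns 2/40 vs 0/40. One might infer that the trial would advance a worthless arm on such a result. The documents do not support that: 13.7 reports the difference with its interval, and 13.8 adds survival, immune-related response and abscopal response. Whether a 5% response rate is worth acting on is a judgement, not a finding about the test. For the same reason, choosing 1.44 over 1.40 is partly a choice about the smallest result that may win.

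**Conclusion.** The point holds in a limited form. Under every reading of the uncorrected test, the exact type I error at the planned 5% rate is above 10%, by 0.2, 1.5 or 2.0 points depending on two conventions that the plan leaves unstated. The rule also counts 2/40 vs 0/40 as a win.

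Separately, 0.56 is not the probability of stopping for futility at the stated boundary, and seems to be a labelling slip for total early stopping. A reader might infer that the correct figure is about 0.65. That holds only if 0/20 vs 0/20 counts as futile, and it is 0.527 otherwise.

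These results assume the pooled statistic without correction, exactly 20 and 40 patients per arm at the two looks, and a common 5% response rate.

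**What to change.** In 13.4.1 and 13.7:
- Set the final cut-off by exact binomial enumeration, or name an exact unconditional test. A cut-off of 1.44 keeps the error below 10% at all common rates examined and requires at least 3/40 against 0/40. A cut-off of 1.40 is a milder option that meets 10% at the planned rate, but it keeps the 2 vs 0 win and can slightly exceed 10% at rates of about 3–4%.
- State that no continuity correction is used, whether futility is binding, and how a 0/20 vs 0/20 interim is handled.
- Restate the exact type I error, power and futility probability under those rules, and relabel or replace the 0.56.

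The cost is wording plus some power. Moving from 1.317 to 1.44 lowers exact power from 83.4% to 80.5% (2.9 points) with futility followed, or from 86.3% to 82.8% (3.5 points) with it non-binding. Both results stay in line with the stated 81%. No extra patients are needed.
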